Objective 2: Individuals consented in the study will complete interviewer-assisted, quantitative study measures at baseline and by 6 months post-study enrollment, including measures of: 1) partner social support;[45] (2) HIV stigma;[46] (3) empathy [47]; (4) HIV knowledge;[48] and (5) patient trust in provider.[49]

Objective 3: Clinical outcomes of the linked models include MTCT risk at birth and weaning, pediatric life expectancy from birth, maternal and paternal life expectancy from presentation to care, and combined (maternal + paternal + pediatric) life expectancy. Economic outcomes, from the healthcare system perspective, include antenatal and postnatal program costs, lifetime maternal HIV-related healthcare costs, lifetime pediatric healthcare costs, and 1 to 5-year maternal and pediatric health care costs. We will use these outcomes to calculate incremental cost-effectiveness ratios (ICERs) in \$/life-year (LY) as the difference in combined healthcare costs (program + maternal lifetime + paternal lifetime + pediatric lifetime costs) between the two strategies, divided by the difference in combined projected life expectancy (maternal + paternal + pediatric life expectancy). For ICERs, all outcomes will be discounted at 3%/year.[79-81] We will consider a strategy to be "cost-saving" if it leads to greater combined life expectancy and lower combined costs than an alternative strategy. Following WHO guidance and evolving consensus in the field of cost-effectiveness analysis, we will consider a strategy to be "cost-effective," compared to its alternative, if its ICER is <0.5-1.0x Mozambique *per-capita* gross domestic product (GDP: \$525 in 2015)/LY. Recognizing the limitations of this approach, we will also compare ICERs to other HIV interventions in Africa, e.g., first line ART (\$500-\$5,500/LY).[82-86]

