The primary data from the HoPS+ program (Objectives 1& 2) will be used as inputs to the MTCT model. These data will include the proportion of mother-infant pairs accessing each step in the EMTCT cascade under the HoPS+ and SOC service-delivery models: ANC, HIV testing, HIV test results, offer and receipt of ART, viral suppression, delivery in a healthcare facility, and linkage to maternal and pediatric care (including EID) after delivery. Data reflecting the biology of HIV infection, including MTCT risks and HIV disease progression (stratified by CD4 and ART use) will be derived from published data, as in previous work,[71] and will be primarily incorporated into the CEPAC-Pediatric and Adult models. We use published data to inform these parameters because EID and ART program data are limited by small patient numbers and by differential loss to follow-up (i.e., higher MTCT, disease progression, and death among those lost to care).

Cost inputs to the models are derived in two steps. First, we estimate healthcare and non-healthcare resource utilization (RU), including inpatient days, outpatient visits, laboratory and pharmacy, and patient and provider time. Next, we assign a unit cost to each resource used (e.g., cost per inpatient day, or wages per hour of provider time), and calculate total costs as the product of RU*unit cost.[79]

c. Instruments used in the study

We will use the following instruments in the study: (1) partner social support;^[45] (2) HIV stigma;^[46] (3) empathy scale ^[47] (4) HIV knowledge;^[48] and (5) patient trust in provider^[49] (see Appendix 2). These instruments are quantitative scales, which provide closed ended options for patient response. We will also utilize the Patient Health Questionnaire (PHQ-9) depression screening tool ^[87] with all participating adult patients (Appendix 3). This instrument is also a quantitative scale with closed ended response options; scores collected at baseline and 6 months will be used as covariate variables in data analysis (see Section 10).

d. Anticipated end date of study:

This study is expected to be concluded in June 2022.

9. Locations of Study

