reporting bias.[95] Specific to this objective, SEM yields precise estimates of mediating and moderating relationships that adjust for the presence of all other variables in the model, more precisely capturing the complex reality of these processes. Direct (including controlled and natural), indirect (including natural), and total effects of the intervention through the mechanisms identified in Aim 2a will be estimated. Further, SEM allows for the flexible respecification and modeling of alternative mediating pathways, such as whether improved levels of social support may be associated with reduced stigma, which is in turn predictive of retention.[94] It also allows for exploring the impact of omitted variables, providing a post-hoc estimate of how robust the parameter estimates are.

Objective 3: The MTCT model is a simulation model of a cohort of pregnant women, from the time of conception through delivery. The model is a deterministic model, with a decision-tree structure, coded in TreeAgePro® software (Williamstown, MA); validation and sensitivity analyses are published.[72, 73, 96-98] Modeled events include the key steps in the EMTCT "cascade of care:" presentation to ANC; offer and acceptance of HIV testing; receipt of HIV test results; offer of, acceptance of, and adherence to ART; maternal mortality during pregnancy; HIV testing in labor for women with unknown/negative HIV status; live birth; infant HIV infection at delivery; and linkage to postnatal care and ART for mothers and infants.[99] After delivery, model outcomes for infants include vital status and HIV infection/exposure (infected, exposed-uninfected, or unexposed); model outcomes for mothers include vital status, CD4 (> or \leq 350/ μ L) and current ART receipt. These outcomes at the time of delivery are translated into long-term survival, life expectancy, and costs by simulating the lifetimes of mothers, fathers and infants in the CEPAC models.

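### Objective 3 gives no determinate verdict for an ICER between 0.5 and 1.0 times GDP per capita, and describes no step that carries the trial's sampling error into the ICER

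*Combined protocol and SAP*

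**What the plan says.** Question 4 (section 6) asks whether the intervention is cost-effective and whether the Ministry of Health would be willing to scale it up. Section 8b, Objective 3, defines the ICER as the difference in combined costs (program plus maternal, paternal and pediatric lifetime costs) over the difference in combined life expectancy. A strategy counts as cost-effective, "compared to its alternative, if its ICER is <0.5-1.0x Mozambique" per-capita GDP, with $525 given for 2015. The same paragraph concedes that this approach has limits and adds: "we will also compare ICERs to other HIV interventions in Africa, e.g., first line ART", with a range of $500-$5,500 per life-year.

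On inputs, section 8b says that the trial data "will be used as inputs to the MTCT model", namely the proportions reaching each step of the care cascade under each service model. Section 8a adds that resource use will be collected in both arms.

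On the models, section 10 (Objective 3) says of the MTCT model: "The model is a deterministic model, with a decision-tree structure". Its only remark on sensitivity analysis is that "validation and sensitivity analyses are published". CEPAC-Adult is described as a first-order, patient-level simulation, and CEPAC-Pediatric as a Monte Carlo simulation.

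**The concern.** Two separate gaps affect the answer to Question 4.

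First, the threshold is a two-fold range used as if it were a single cut-off. Within that range the plan does not determine the verdict, so whoever writes the report has to choose an end, possibly with the ICER already in view.

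Second, the cascade proportions and resource use come from 24 clinics, 12 per arm, and will be estimated with error that clustering enlarges. A deterministic model turns point inputs into a point output. A first-order simulation reproduces variation between individuals; it does not reflect uncertainty about the input parameters. Followed as written, the plan delivers an ICER with no interval and a verdict with no statement of how secure it is. Scale-up advice would rest on that number.

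**Working it through.** **Threshold (document figures only).** 0.5 × $525 = $262.50 and 1.0 × $525 = $525, a ratio of 2.

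| ICER per life-year | At 0.5× | At 1.0× | Verdict under the plan |
|---|---|---|---|
| below $262.50 | pass | pass | cost-effective |
| $262.50 to just under $525 | fail | pass | not determined |
| $525 or more | fail | fail | not cost-effective |

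The second benchmark does not settle the middle row. It spans 5,500/500 = 11-fold, its lower end ($500) lies inside the undetermined band, and no conclusion is tied to it.

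**Is there a step for uncertainty?** Sections 8a, 8b and 10 describe, for Objective 3, the inputs, three linked models, discounting and the ICER. They mention no interval, resampling, probabilistic sensitivity analysis or acceptability curve. The published sensitivity analyses were done before this trial and cannot reflect its inputs. By contrast, section 10 gives Objective 1 a clinic random effect, and gives infant infection a sensitivity analysis with multiple imputation.

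**How large might the uncertainty be?** The plan states no ICER and no ICC, so this part is an illustration.

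Inputs from section 7d: 24 clusters of 45 couples, so 12 × 45 = 540 women per arm; ART initiation 55% against 71.5% (0.55 × 1.30 = 0.715), a difference of 16.5 points. (Section 7e stops enrolment at 40 per site; 45 is used here.) Assumed: ICC 0.02 or 0.05, and a point ICER of $350. Both ICCs fit the plan's claim of over 80% power: with a design effect of 1 + 44 × ICC and two-sided 0.05, power is 98.5% at 0.02, 88.5% at 0.05, and falls to 80% near 0.07.

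Standard error of the difference: √[(1 + 44 × ICC) × (0.55 × 0.45 + 0.715 × 0.285)/540].

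- ICC 0.02: √(1.88 × 0.4513/540) = 0.0396. With t(22) = 2.074, the 95% interval is 8.3 to 24.7 points.
- ICC 0.05: √(3.20 × 0.4513/540) = 0.0517, giving 5.8 to 27.2 points.

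Let life-years gained be proportional to the effect e, with planned value d = 16.5 points. Let a share s of incremental cost also be proportional to e, the rest being fixed. Then ICER(e) = ICER(d) × [s + (1 − s) × d/e]. At ICC 0.02, d/e runs from 16.5/24.7 = 0.668 to 16.5/8.3 = 1.99. At ICC 0.05 it runs from 0.61 to 2.86.

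| Point ICER $350 | s = 0 (cost fixed) | s = 0.5 |
|---|---|---|
| ICC 0.02 | about $234-$697 | about $292-$523 |
| ICC 0.05 | about $212-$1,000 | about $281-$675 |

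For example, with s = 0.5 and ICC 0.02 the upper limit is 350 × (0.5 + 0.5 × 1.99) = $523. Rounding moves these figures by a dollar or so.

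With cost fixed, the range covers both limits. With half of the cost scaling, it covers neither at ICC 0.02 and only the upper one at ICC 0.05. The $523 is close to $525 and sensitive to method: using t(11) = 2.201, as for 12 pairs, with the same standard error, the lower effect limit is 0.165 − 2.201 × 0.0396 = 0.0778. The multiplier is 0.165/0.0778 = 2.12 and the upper limit 350 × (0.5 + 0.5 × 2.12) = $546.

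**The case against.** The best defence has four parts.

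- **The effect on the verdict may be small.** A reader might infer that the uncertainty exceeds the threshold band, or that any result could be declared either way. The documents support neither. The wide ranges come from holding incremental cost fixed, whereas section 8b puts lifetime care costs in the numerator, and these would be expected to rise as more people start and stay on ART. The $350 point also matters: with cost fixed and ICC 0.02, only point ICERs from roughly 525/1.99 = $264 to 262.50/0.668 = $393 have a range that covers both limits. The plan gives no expected ICER. This objection stands.
- **The GDP rule is not the only yardstick.** The plan concedes its limits and adds a second comparison. That is true and to its credit, but the comparison has no rule.
- **Silence is not refusal.** The plan nowhere says that uncertainty will be ignored, or that the threshold will be picked after the fact. A reader might also infer that the threshold is frozen at 2015 GDP; the figure may be only illustrative. These points stand too. What remains is that no method, no deciding rule and no common price year is stated, for a study expected to end in June 2022 (section 8d).
- **Trial sampling error is only part of the uncertainty.** Transmission risks, disease progression and long-term costs come from published data. This also stands, and it shapes the remedy.

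**Conclusion.** The concern holds in a bounded form. The indeterminate verdict between $262.50 and $525 per life-year follows from the plan's own figures and needs no assumption. The missing step for input uncertainty is an omission in the Objective 3 text. How much it matters numerically cannot be derived from the documents. It depends on the ICC, the point ICER and the share of incremental cost that moves with effect, none of which is given; the illustrations also let life-years follow the initiation effect alone. For $350 at ICC 0.02 they give about $234-$697 or about $292-$523, depending on the cost assumption. It is therefore not shown that the uncertainty is wider than the band. Objectives 1 and 2 are unaffected. The point should be settled before the trial data enter the models, because Question 4 is meant to inform scale-up.

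**What to change.** 1. Before the ICER is known, state how the verdict follows from the two limits. One option is cost-effective below 0.5×, not cost-effective above 1.0×, and threshold-dependent between them. Choosing a single limit instead is a policy decision that the documents do not settle. Express costs and GDP in one stated price year.
2. Resample the 12 matched clinic pairs. In each draw, re-estimate the arm-specific cascade and resource-use inputs jointly and run the linked models.
3. Vary the published inputs (transmission, progression, long-term costs) in planned sensitivity analyses, since resampling clinics does not cover them.
4. Beside the point verdict, report the ICER uncertainty interval and the probability that the ICER is below 0.5× and below 1.0× GDP per capita, and say which sources of uncertainty those figures include.

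No new data are needed. The cost is model run time, some added text in the analysis plan, and a conclusion that may be less definite.

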Objective 2: Aim 2 analyses will utilize a subset of the 1,080 enrolled couples (2,160 individuals) who are alive and can be contacted to provide data by 6 months after enrollment, regardless of whether or not they are retained in care. Because the psycho-social data collected by 6 months may be influenced by whether or not participants were retained through 6 months, our analyses will initially only consider retention outcomes after 6 months to maintain the temporal order needed to infer any mediation effects.

e. Sampling

Participants: HIV infected couples will be enrolled for 6 months at each study site. Patients will be enrolled on a first come, first enrolled basis until 40 couples have been enrolled.

[figure not shown]
f. Patient participant retention and withdrawal:

As per standard clinic procedure, couples on the control arm will receive separate clinical services at the ANC building and the adult HIV clinic, respectively. Peer educators will track all clients who miss appointments at control and intervention sites. The Home Based Care workers will document clients as terminating care if they: (1) discontinued services due to death; (2) transferred their care to another clinic that is not in the study; (3) are lost to follow-up (defined as being >90 days late for a clinic appointment plus 3 failed attempts at tracking the client); or (4) discontinue for any other reason, including patient choice. Clients will not receive any remuneration for participating in the study, per Mozambican National Medical Ethics Committee, but interview participants will be provided a small snack. Clients will be allowed to discontinue participation and may decide that their medical data cannot be used in the analysis at any time during the study.

8. Methods

a. Study Procedures

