For this project, de-identified data will be extracted into a restricted dataset by FGH employees from the existing OpenMRS databases and sent to a VUMC Biostatistician for analysis. All routine programmatic data are owned by the MOH. All routine programmatic data are part of the clinical record and as such will not be destroyed.

Data Analysis

Objective 1: Statistical analysis plan for Objective 1. We propose a generalized linear mixed effects model, with random effect for clinic.[88] A simple model for $E(Y_{ij})$, the probability of ART initiation in the i th clinic at the j th time-point is given by:

$$\text{logit } E(Y_{ij}) = \beta_1 + \beta_2 \text{Group}_{ij} + b_i + e_{ij}$$

where b_i is a random effect for clinic i which accounts for clustering of patients within clinics, due perhaps to similarities in health-seeking behavior and/or access to care. β_1 is a fixed effect

corresponding to time j , $Group_{ij}$ is an indicator of intervention, and β_2 is the treatment effect (difference in log odds of ART receipt). We test the hypothesis, $H_0: \beta_2 = 0$. The mixed effects model will be extended to allow for covariate adjustment, such as: age, education, and distance from clinic. Separate models will be used to assess each outcome in each population (men, women, infants). For example, ART initiation among pregnant women ($n=1,080$) and then ART initiation among male partners ($n=1,080$). All adult patient models will include depression scale scores as covariates in attempts to control for potential presence of depression symptoms among participant groups. Female-specific models allow for inclusion of covariates unique to pregnant women, such as prior ANC, parity, etc. We also expect the intervention odds ratio to differ between women and their male partners. For infant HIV infection, sensitivity analyses will be conducted to investigate the effect of no EID test result on HIV infection; infants of mothers who did not initiate ART or were not retained in care at delivery will be assigned probabilities of infection (with definitions based on latest research). Then, infant HIV status will be multiply imputed using the Bernoulli distribution and estimates from the multiple regressions will be combined with multiple imputation techniques. An intent-to-treat approach will be employed for all analyses.

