Due to the potential for false positive results when many comparisons are performed, we will report test results in all abstracts, manuscripts, and presentations in a pre-determined order as ascertained by the HoPs+ investigators. For example, the order of reporting results could be male initiation, male retention, female initiation, female retention, etc.; the final order will be selected *a priori*. Because we are interested in answering multiple questions but will report all analyses in the context of the aforementioned ordering, no adjustment for multiplicity will be performed, an approach consistent with recommendations for clinical trials.[89] Analyses will be conducted using R software (www.r-project.org), and scripts will be accessible on our Vanderbilt project website.

Objective 2: Generalized linear mixed effects model will be utilized as described for Objective 1, replacing the logit transformation of the outcome with an untransformed linear outcome because the outcomes are continuous. Intervention status remains the exposure variable of interest and β_2 is the treatment effect (difference in mean levels of knowledge, stigma, etc.). As with Objective 1, gender specific models will be used to model each outcome of interest, adjusting for individual level covariates such as age, education, depression scores, and distance from clinic. Interactions between intervention status and the baseline value of each endpoint will be used to assess for modification of the intervention effect. All potential mediators found to be associated with the intervention at $p<0.20$ in Objective 2 will be included in a multi-level structural equation model (SEM) to account for clustering within clinics (Figure 2). SEM is well-suited to examining mediating and moderating processes over time [90-94]. Specification of the potential mediators as latent variables in SEM allows for better specification of measurement error, potentially reducing bias.[91, 94] Further, the capacity to detect and adjust for potential reporting bias in key study measures (e.g., does social desirability lead male partners to systematically report lower stigma) ensures that true differences in parameter estimates are not inflated by

Version 2

[figure not shown]

Figure 2: Mechanisms of Intervention Effect

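### The 6-month PHQ-9 score, taken after months of intervention, is a named covariate, and nothing in the plan keeps it out of the adult treatment-effect models

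*Combined protocol and SAP*

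**What the plan says.** Section 8c (Instruments) introduces the PHQ-9 for all participating adults and states that "scores collected at baseline and 6 months will be used as covariate variables in data analysis", with a cross-reference to Section 10.

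Section 10 mentions depression scores twice:

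- Objective 1: "All adult patient models will include depression scale scores as covariates", and the reason given is "in attempts to control for potential presence of depression symptoms among participant groups".
- Objective 2: the models for knowledge, stigma and the other scales are fitted "adjusting for individual level covariates such as age, education, depression scores, and distance from clinic".

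Neither sentence gives a time point. In both objectives Section 10 calls β₂ the treatment effect: a difference in log odds for Objective 1 and a difference in means for Objective 2. For Objective 1 it tests H₀: β₂ = 0, and it promises intention to treat for all analyses.

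The Objective 2 results also feed a selection step: "All potential mediators found to be associated with the intervention at" p<0.20 enter the structural equation model (SEM). The SEM text does not mention depression.

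Section 7d, on Objective 2, recognises that psychosocial data collected by 6 months may depend on retention up to then. It therefore says "our analyses will initially only consider retention outcomes after 6 months to maintain the temporal order needed to infer any mediation effects".

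**The concern.** A covariate in a treatment-effect model should not be something the treatment can alter. The 6-month PHQ-9 can be altered: by then a couple in the intervention arm has had peer mentoring from the first week and counselling every other month (Section 8a). Depression is not among the five hypothesised mechanisms, and no document predicts that PHQ-9 will move. Section 11, however, foresees both possible extra psychosocial support and potential interpersonal conflict, so a shift in either direction is plausible.

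If the score shifts and is related to the outcome, β₂ becomes a conditional contrast and not the total effect of assignment. The direction of the difference cannot be known in advance. For ART initiation the score will usually be measured after the outcome has occurred. For Objective 2 a distorted β₂ can also change which mediators reach the SEM. And because the time point is open, it could be chosen after the data are seen.

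**Working it through.** **1. Following the cross-reference.** Section 8c names two time points and sends the reader to Section 10. Section 10 uses depression scores only in the effect models. Its one reference to a baseline value concerns interactions with the baseline level of each Objective 2 endpoint, not PHQ-9. The Section 7d safeguard is written for the mediation analysis. It covers neither the Objective 1 models nor the Objective 2 effect models, whose outcomes are themselves collected by 6 months (Section 8b). Read as written, the 6-month score belongs in the adult effect models. The infant models are not stated to carry it.

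**2. The plan's own effect sizes (Section 7d).** These reproduce: 0.55 × 1.30 = 0.715; 0.55 × 0.56 = 0.308; 0.715 × 0.56 × 1.2 = 0.480. The crude odds ratios (OR) are

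- retention: (0.48/0.52)/(0.31/0.69) = 2.05
- ART initiation: (0.715/0.285)/(0.55/0.45) = 2.05

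Every PHQ-9 input below is an assumption. The baseline to 6-month correlation is taken as 0.5. The logistic results come from simulations with N = 1,000,000 and no clinic random effect.

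**3. Retention.** 6-month PHQ-9 = 0.5 × baseline + shift × arm + noise, with the intercept and direct effect set to give 31% vs 48%. The slope is the log OR for retention per SD of PHQ-9. With the baseline score only, OR = 2.07 and the risk difference (RD) is 17 points. Adding the 6-month score gives:

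| Shift in PHQ-9 (SD) | OR (RD), slope −0.3 | OR (RD), slope −0.5 |
|---|---|---|
| −0.5 | 1.80 (13.6) | 1.67 (11.4) |
| −0.2 | 1.97 (15.7) | 1.94 (14.8) |
| 0 | 2.10 (17.1) | 2.14 (17.0) |
| +0.2 | 2.22 (18.4) | 2.37 (19.2) |
| +0.5 | 2.44 (20.5) | 2.76 (22.4) |

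At zero shift the RD does not change. The small rise in OR there is non-collapsibility, not bias.

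**4. ART initiation.** Here the score follows the outcome: 6-month PHQ-9 = 0.5 × baseline + d × arm − k × initiated + noise. With the baseline score only, OR = 2.05. Adding the 6-month score gives:

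| d (SD) | k = 0 | k = 0.2 | k = 0.4 |
|---|---|---|---|
| −0.5 | 2.05 | 1.80 | 1.57 |
| −0.2 | 2.05 | 1.94 | 1.84 |
| 0 | 2.05 | 2.05 | 2.05 |
| +0.2 | 2.04 | 2.16 | 2.28 |
| +0.5 | 2.04 | 2.34 | 2.67 |

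**5. Objective 2 and the p<0.20 screen.** In a linear model, adjusted effect = total effect − slope × shift. With a true effect of 0.15 SD and a slope of −0.3 on 6-month PHQ-9, this is 0.15 + 0.3 × shift.

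SE = √(4 × DE/1080), where DE = 1 + 44 × ICC. ICC 0.01 gives DE 1.44 and SE 0.073; ICC 0.05 gives DE 3.20 and SE 0.109. The two-sided cut-off is 1.2816 (normal approximation).

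| Shift (SD) | Adjusted effect (SD) | P(pass), ICC 0.01 | P(pass), ICC 0.05 |
|---|---|---|---|
| −0.5 | 0.00 | 0.20 | 0.20 |
| −0.2 | 0.09 | 0.49 | 0.34 |
| 0 | 0.15 | 0.78 | 0.54 |
| +0.2 | 0.21 | 0.94 | 0.74 |
| +0.5 | 0.30 | >0.99 | 0.93 |

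The same formula shows what happens to the null hypothesis. With a total effect of zero and a shift of ±0.5 SD, the adjusted effect is ±0.15 SD.

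**6. No causal effect of PHQ-9 is needed.** Suppose PHQ-9 does not affect retention but shares an unmeasured cause with it (assumed loading 0.5 on the score, −0.7 on the log odds of retention). In a simulation with retention of about 31% vs 46%, adding the 6-month score takes β₂ from 0.65 to 0.54 when the intervention lowers PHQ-9 by 0.3 SD, and from 0.66 to 0.46 at 0.5 SD.

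**The case against.** The strongest reply is that the harmful model is inferred. Section 8c does not say which score enters which model, and Section 10 also contains an SEM in which a 6-month score could belong. That reading is possible but written nowhere: the SEM text never mentions depression, while the effect-model text does.

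Second, β₂ and its test are introduced for a simple model without covariates. This is so, but Section 10 then extends that model and puts depression scores into all adult models.

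Third, every PHQ-9 input is assumed, the results include no bias, and if the intervention moves neither PHQ-9 nor the outcome then β₂ stays at zero. All of this stands. The figures are illustrations, not estimates for this trial. They omit the clinic random effect, and step 5 uses all 1,080 people per sex although Section 7d limits Objective 2 to those alive and contactable.

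Two points of timing also stand. Clinics are randomised and couples are enrolled afterwards, so the baseline score may follow randomisation too; what separates the two scores is months of exposure. And ART enrolment at diagnosis is described for HoPS+ (just before Section 5), so the timing of initiation in control clinics is less certain.

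None of this removes the defect, which is that the plan does not fix which effect β₂ estimates.

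**Conclusion.** The concern holds. Section 8c makes the 6-month PHQ-9 a covariate, and Section 10 does not confine the adult effect models to baseline. If the intervention shifts that score and the score is related to the outcome, β₂ may not be the total effect of assignment.

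Under the stated assumptions, the retention OR of 2.07 could become 1.67 to 2.76 (RD 11.4 to 22.4 points against 17), and the initiation OR of 2.05 could become 1.57 to 2.67. An Objective 2 mediator's chance of passing the screen could fall from 0.78 to 0.20 or rise above 0.99 at ICC 0.01. With no shift in PHQ-9 there is no bias. The true size cannot be derived from the documents.

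Grouping by assigned arm is unaffected. However, if the 6-month PHQ-9 is available only for people alive and contactable (assumed, by analogy with the Objective 2 surveys), a complete-case fit would drop participants whom Section 7d counts as failures. That would conflict with intention to treat. The wording must be corrected before the analysis.

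**What to change.** Reword Section 8c along these lines: *The baseline PHQ-9 score will be a covariate in the Objective 1 and Objective 2 treatment-effect models (Section 10); the 6-month score will not be a covariate in those models.* In Section 10, replace the two unspecified references to depression scores (Objective 1 and Objective 2) with the baseline PHQ-9 score. If the 6-month score is wanted in the SEM or in a sensitivity analysis, name that use separately and do not call the resulting coefficient the treatment effect.

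The cost is a wording change in three places. Baseline PHQ-9 is already planned for all participating adults, so no data, visits or participants are added. The stated aim of controlling for depression symptoms across the groups can be served by the baseline score.
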